8.2. Secondary Efficacy Endpoint

8.2.1. Achieved CDA without CS within 4 Weeks

- The proportion of patients who are able to achieve CDA without CSs within 4 weeks will be summarized in the same way as that described in Section 8.1. Patients who are able to achieve CDA by the Week 5 visit and have no occurrence of any CS on or before the first CDA visit during the study treatment will be considered as responders. Patients who are not able to achieve CDA by the Week 5 visit or have any occurrence of any CS on or

before a CDA visit during the study treatment will be considered as non-responders. Patients whose CDA status is unknown at the Week 5 visit for whatever reason (include early termination before Week 5 visit) will be also considered as non-responders. Only systemic CSs (as defined by medication taken orally or intravenously) are to be used to evaluate the efficacy endpoints, topical CSs will not be counted.

8.2.2. Achieved CR without CS within 12 Weeks

The proportion of patients who are able to achieve CR without CSs within 12 weeks will be summarized in the same way as that described in Section 8.1. Patients who are able to achieve CR between treatment start date and the Week 13 visit and have no occurrence of any CS after the treatment start date and before the first CR visit during the study treatment will be considered as responders. Patients who are not able to achieve CR between start of treatment and the Week 13 visit or have any occurrence of any CS between start of treatment and a first CR visit during the study treatment will be considered as non-responders. Patients whose CR status is unknown at the Week 13 visit for whatever reason (include early termination before Week 13 visit) will be also considered as non-responders. Only systemic CSs (as defined by medication taken orally or intravenously) are to be used to evaluate the efficacy endpoints, topical CSs will not be counted.

8.2.3. Achieved CR without Prednis(ol)one >0.5 mg/kg within 12 Weeks

The proportion of patients who are able to achieve CR without the need for doses of prednis(ol)one of greater than 0.5 mg/kg within 12 weeks will be summarized in the same way as that described in Section 8.1. Patients who are able to achieve CR at any visit on or before the Week 13 visit during the study treatment and have no occurrence of daily prednis(ol)one >0.5 mg/kg between the first dose date of PRN1008 treatment and the day before the date of the first CR will be considered as responders. Patients who are not able to achieve CR at all visits on or before the Week 13 visit during the study treatment or have any occurrence of daily prednis(ol)one >0.5 mg/ between the first dose date of PRN1008 treatment and the day before the date of the first CR will be considered as non-responders. Patients whose CR status is unknown at all visits on or before Week 13 visit during the study treatment for whatever reason (include early termination before Week 13 visit) will be also considered as non-responders. Only systemic CSs (as defined by medication taken orally or intravenously) are to be used to evaluate the efficacy endpoints, topical CSs will not be counted.

8.2.4. Proportion of CDA and CR at each Visit

The proportion of patients who are able to achieve CDA and the proportion of patients who are able to achieve CR will be summarized by maximum dose level and overall by CDA and CR status for each visit by using frequencies and percentages, respectively. This is a cross sectional analysis and differs from the cumulative assessment of efficacy described above. In addition, two-sided 80% and 95% CIs of the response rate will be provided for each maximum dose level and overall using the Exact (Clopper-Pearson) method.

The proportion of patients who are able to achieve CDA and/or CR without the need for doses of prednis(ol)one of greater than 0.5 mg/kg (CS doses from Day 1 to the day before the date of the visit) will also be summarized by maximum dose level and overall for each visit. Two-sided 80% and 95% CIs will be provided by using the Exact (Clopper-Pearson) method.

The disease status at each visit, and the CS dose on the day before the achievement date will be listed.

8.2.5. Cumulative Incidents of CDA and CR at each Visit

The cumulative incidents of patients who are able to achieve CDA and CR by each visit will be summarized by maximum dose level and overall. This is a cumulative analysis compared to section 8.2.4. In addition, two-sided 80% and 95% CIs of the response rate will be provided for each maximum dose level and overall using the Exact (Clopper-Pearson) method.

The proportion of patients who are able to achieve CDA and/or CR without the need for doses of prednis(ol)one of greater than 0.5 mg/kg (CS doses from Day 1 to the day before the date of the visit) will also be summarized by maximum dose level and overall for each visit. Two-sided 80% and 95% CIs will be provided by using the Exact (Clopper-Pearson) method.

If a subject drops out, they will still accommodate to future unattended visits cumulatively, i.e. the denominator for this analysis would not diminish over time.

8.2.6. Time to first CDA, CR, End of Consolidation Phase, and Relapse

Time to first CDA is defined as the following:

$$\text{Time to first CDA} = \text{Date of the first CDA confirmed} - \text{Date of first dose} + 1.$$

Time to first CR and End of Consolidation Phase are defined in the same way as Time to first CDA.

Time to first relapse after PRN1008 treatment completion or discontinuation is defined as the following:

$$\text{Time to first Relapse} = \text{Date of the first relapse after Week 13 visit confirmed} - \text{Date of last PRN1008 dose} + 1.$$

If the date of last PRN1008 dose is missing, the date of the Week 13 visit during treatment will be used. If patients did not complete the Week 13 visit they will be excluded from the relapse analysis.

The time to relapse analysis will be conducted in two subpopulations for each analysis population: 1) Patients with CDA at the Week 13 visit, 2) Patients with CR at the Week 13 visit.

Patients who have not achieved the above events by the date of study completion or discontinuation will be censored at the date of completion or discontinuation respectively.

Kaplan-Meier survival distribution plots for time to each event will be provided. Kaplan-Meier estimates of quartiles in days and its associated 80% and 95% CI will be calculated by using the LOGLOG transformation. Min and Max survival times in days as well as number of the patients and the probability of experiencing the event on or before specific date will be provided in a table.

The CDA status, CR status, End of Consolidation Phase status, and Relapse status by visit, by patient will be presented in a listing.

Duration of CR will be summarized and listed, and is defined by the last known CR date – first known CR date + 1. Each subject will only have one CR date as a result.

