11.2 Secondary Outcome Measures

The following clinical activity endpoints* will be assessed:

- Proportion of subjects able to achieve CDA without corticosteroids within 4 weeks
- Proportion of subjects able to achieve a complete response (CR) without corticosteroids within 12 weeks (and 24 weeks in **Part B**)
- Proportion of subjects able to achieve CR without the need for doses of prednis(ol)one of greater than 0.5mg/kg within 12 weeks (and 24 weeks in **Part B**)
- Time to CDA
- Time to CR
- Time to end of consolidation phase
- Time to relapse after PRN1008 treatment discontinuation
- Cumulative corticosteroid usage over the first 12 weeks (and 24 weeks in **Part B**)
- Change from baseline in Pemphigus Disease Area Index (PDAI) and Autoimmune Bullous Skin Disorder Intensity Score (ABSIS) scores at each follow-up visit
- Change from baseline in Autoimmune Bullous Diseases Quality of Life (ABQOL) and Treatment of Autoimmune Bullous Diseases Quality of Life (TABQOL) scores at each follow-up visit
- Change from baseline in appetite (SNAQ score) at each follow-up visit

*Clinical activity endpoints as defined by the EADV 2014 pemphigus S2 guideline ([Hertl et al. 2015](#)) with the exception that CR is defined as CR at a single point in time rather than present for ≥ 2 months

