3.2.3. Secondary Efficacy Endpoints

- Proportion of patients able to achieve CDA without CSs within 4 weeks
- Proportion of patients able to achieve a complete response (CR) without CSs within 12 weeks
- Proportion of patients able to achieve CR without the need for doses of prednis(ol)one of greater than 0.5 mg/kg at any point within 12 weeks
- Proportion of patients able to achieve CDA at each visit
- Proportion of patients able to achieve CDA at each visit with or without the need for doses of prednis(ol)one of greater than 0.5 mg/kg
- Cumulative incidence of patients ever achieved CDA by each visit
- Cumulative incidence of patients ever achieved CDA by each visit with or without the need for doses of prednis(ol)one of greater than 0.5 mg/kg

- Proportion of patients able to achieve CR at each visit
- Proportion of patients able to achieve CR at each visit with or without the need for doses of prednis(ol)one of greater than 0.5 mg/kg
- Cumulative incidence of patients ever achieved CR by each visit
- Cumulative incidence of patients ever achieved CR by each visit with or without the need for doses of prednis(ol)one of greater than 0.5 mg/kg
- Time to first CDA
- Time to first CR
- Time to first end of consolidation phase
- Time to first relapse after PRN1008 treatment completion or discontinuation
- Cumulative CS usage over 12 weeks
- Change from baseline in Pemphigus Disease Area Index (PDAI) and Autoimmune Bullous Skin Disorder Intensity Score (ABSIS) scores at each follow-up visit
- Change from baseline in Autoimmune Bullous Diseases Quality of Life (ABQOL) and Treatment of Autoimmune Bullous Diseases Quality of Life (TABQOL) scores at each follow-up visit
- Change from baseline in appetite (SNAQ score) at each follow-up visit

CR, End of consolidation phase, and Relapse as defined in European Academy of Dermatology and Venereology (EADV) 2015 Pemphigus S2 Guideline are listed below:

Complete response (CR) is defined as the absence of new or established lesions while the patient is receiving minimal or no non-PRN1008 immunotherapy. In this study, “minimal therapy” is defined as daily doses of ≤ 10 mg of prednisolone or equivalent doses of other CS for any period of time.

End of consolidation phase: The time at which no new lesions have developed for minimum of 2 weeks, approximately 80% of lesions have healed, and when most clinicians start to taper steroids.

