Relapse/flare: Appearance of ≥ 3 new lesions/month that do not heal spontaneously within 1 week, or by extension of established lesions, in a patient who has achieved disease control.

Only patients with confirmed CDA before treatment completion or discontinuation will be included into this analysis.

[1] Time to first relapse = Date of first relapse confirmed after Week 13 - Date of last dose + 1. Patients who did not achieve relapse between Week 13 visit and the date of study completion or discontinuation were censored at the date of completion or discontinuation respectively. 80% and 95% confidence intervals are calculated using the LOGLOG transformation.

[2] * indicate that this value is from a censored data.

[3] Kaplan-Meier estimate of the probability of experiencing the event on or before the specified timepoint (n' = number of patients remaining at risk beyond the specified timepoint).

Source Data: Listing 16.2.4.1.9

<DIRECTORY PATH>PROGRAM NAME Executed: DDMMYYYY hh:mm

Prog note: Repeat for 2) Patients with CR at the Week 13 visit in the same table, and change the first row accordingly.

Repeat the above table with all the subpopulations using the following analysis populations.

Table 14.2.3.4.2

Time to First Relapse after PRN1008 Treatment Completion or Discontinuation Among Subjects who Achieved CDA
at Week 13 Visit: Kaplan Meier Estimates
mITT Population

Table 14.2.3.4.3

Time to First Relapse after PRN1008 Treatment Completion or Discontinuation Among Subjects who Achieved CDA
at Week 13 Visit: Kaplan Meier Estimates
Per Protocol Population

Table 14.2.4.1.1
 Cumulative Corticosteroid Usage over 12 Weeks
 ITT Population

Cumulative Corticosteroid Usage (mg)	400 mg (N=xx)	500 mg (N=xx)	600 mg (N=xx)	Total (N=xx)
n	xx	xx	xx	xx
MEAN (SD)	xxx.x (xxx.xx)	xxx.x (xxx.xx)	xxx.x (xxx.xx)	xxx.x (xxx.xx)
MEDIAN	xxx.x	xxx.x	xxx.x	xxx.x
MIN, MAX	xxx, xxx	xxx, xxx	xxx, xxx	xxx, xxx

Note: Patients are classified into different dose levels according to the maximum dose they received during the 12 week treatment period.
 Patients who have completed at least Week 13 Visit are included.
 All corticosteroids were converted into prednisolone. Each 10 mg of prednisolone is equivalent to 10 mg of prednisone, 8 mg of methylprednisolone, 1.5 mg dexamethasone, 40 mg hydrocortisone or 1.5 mg betamethasone.
 Source Data: Listing 16.2.3.1
 <DIRECTORY PATH>PROGRAM NAME Executed: DDMMYYYY hh:mm

Repeat the above table using the other populations

Table 14.2.4.1.2

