 End of consolidation phase: The time at which no new lesions have developed for minimum of 2 weeks, approximately 80% of lesions have healed, and when most clinicians start to taper steroids.
 Time to first end of consolidation phase = Date of first end of consolidation phase confirmed - Date of first dose + 1. Patients who did not achieve end of consolidation phase by the date of study completion or discontinuation were censored at the date of completion or discontinuation respectively.

<DIRECTORY PATH>PROGRAM NAME Executed: DDMMYYYY hh:mm

Prog Note: Sort by Maximum Dose Level (400 mg, 500 mg, 600 mg, missing), Patient ID, Visit.

Listing 16.2.4.1.9

Time to First Relapse after Week 13 Visit
 ITT Population

Maximum Dose Level: XXX mg

Patient ID	Age (yrs) / Sex / Race	Analysis Set	First Dose Date / Last Dose Date	Date of First Relapse After Week 13 or Censored Date	CDA at Week 13	CR at Week 13	Time to First Relapse From Week 13 (Days)	Censored
XXXXXX	50/M/W	Safety/ Efficacy	DDMMYYYY / DDMMYYYY	DDMMYYYY	Yes/No	Yes/No	xx	Yes
				DDMMYYYY	Yes/No	Yes/No	xx	Yes
				DDMMYYYY	Yes/No	Yes/No	xx	Yes
				DDMMYYYY	Yes/No	Yes/No	xx	No
							...	
							...	

Note: Sex: M=Male, F=Female; Race: W=White, BL=Black or African American, AS=Asian, AI=American Indian or Alaska Native, PI=Native Hawaiian or Other Pacific Islander, O=Other, FSNC=French Sites Only - Not Collected
 Relapse/flare: Appearance of >=3 new lesions/month that do not heal spontaneously within 1 week, or by extension of established lesions, in a patient who has achieved disease control. Only patients with confirmed CDA before treatment completion or discontinuation will be included into this listing.
 Time to first relapse = Date of first relapse confirmed after week 13 - Date of week 13 visit + 1.
 Patients who did not achieve relapse by the date of study completion or discontinuation were censored at the date of completion or discontinuation respectively.

<DIRECTORY PATH>PROGRAM NAME Executed: DDMMYYYY hh:mm

Prog Note: Sort by Maximum Dose Level (400 mg, 500 mg, 600 mg, missing), Patient ID, Visit.

Listing 16.2.4.1.10

Duration of Complete Response (CR) Status Among CR Subjects
 ITT Population

Maximum Dose Level: XXX mg

Patient ID	Age (yrs) / Sex / Race	Analysis Set	CR Start Date	Last Known CR Date	Last Follow up Date	Duration [1]
XXXXXX	50/M/W	Safety/ Efficacy	DDMMYYYY	DDMMYYYY	DDMMYYYY	Xx
XXXXXX	32/F/W	Safety/ Efficacy	DDMMYYYY	DDMMYYYY	DDMMYYYY	xx

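### Part A's time-to-relapse rule starts the clock at the last dose but counts only relapses after Week 13, so relapse can be understated for patients who stop PRN1008 early

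*SAP*

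**What the plan says.** Protocol 11.2 lists the endpoint as "Time to relapse after PRN1008 treatment discontinuation". Part A SAP 3.2.3 widens the wording to "Time to first relapse after PRN1008 treatment completion or discontinuation", so patients who stop before 12 weeks are in scope by name.

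Part A SAP 8.2.6 sets the rule:

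- **Event:** "Date of the first relapse after Week 13 visit confirmed".
- **Origin:** date of last PRN1008 dose, plus one day.
- **Exclusion:** "If patients did not complete the Week 13 visit they will be excluded from the relapse analysis".
- **Subpopulations:** "1) Patients with CDA at the Week 13 visit, 2) Patients with CR at the Week 13 visit".

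The output shells do not all follow it:

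- **Table 14.2.3.4.1, footnote:** "Time to first relapse = Date of first relapse confirmed after Week 13 - Date of last dose + 1". Its population note reads "Only patients with confirmed CDA before treatment completion or discontinuation will be included into this analysis", while the table's first row is headed for patients with CDA at Week 13.
- **Listing 16.2.4.1.9**, the table's stated source: "Time to first relapse = Date of first relapse confirmed after week 13 - Date of week 13 visit + 1".
- **Figure 14.2.3.4.1, footnote:** origin at last dose, with no restriction to relapses after Week 13, although the figure names the table as its source.

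**The concern.** The clock can start well before the first day on which an event may be counted. Take a patient who stops in CDA at Week 6 and relapses at Week 9. If that patient misses Week 13, the exclusion applies. If the patient attends but is not in CDA, neither subpopulation includes them. If the patient has regained CDA by Week 13, they are kept and the Week 9 relapse is ignored. In no case is the relapse an event, although it is a relapse after discontinuation.

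A patient who stops at Week 6 and is still in control at Week 13 enters with about seven weeks in which an event was impossible. Timing from last dose while conditioning on control at a later visit is immortal time, and it pushes the curve toward durability.

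This is the only planned time-to-event estimate of relapse off drug. Part B SAP 5.4.2.2 times relapse from the first dose of the dose level. Part A SAP 4.1 says the results will be used to design confirmatory trials.

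**Working it through.** The documents give no relapse rate, event count or precision for this endpoint, so there is no plan figure to reproduce. The check is date arithmetic plus two illustrations whose inputs are assumptions.

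**Inputs from the documents.** Week 13 visit: Day 85 ± 7, that is Day 78 to 92 (Part A SAP 15.1). Planned end of treatment: Day 84 (Part A SAP 3.1) or Day 85 (Protocol 4.3). Kaplan-Meier time points for relapse: 29, 57 and 85 days (Table 14.2.3.4.1).

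**Step 1: guaranteed relapse-free time.** Earliest countable relapse = visit day + 1. Time on the table's clock = relapse day − last dose day + 1. With the visit on Day 85, the relapse day is 86:

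| Last dose | Earliest possible event (days) |
|---|---|
| Day 15 | 86 − 15 + 1 = 72 |
| Day 29 | 86 − 29 + 1 = 58 |
| Day 57 | 86 − 57 + 1 = 30 |
| Day 84 | 86 − 84 + 1 = 3 |
| Day 85 | 86 − 85 + 1 = 2 |

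A Day 29 stopper cannot contribute an event at the 29- or 57-day point. A Day 57 stopper cannot contribute one at 29 days.

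For a completer, the blind interval is last dose to Week 13 visit: at most 92 − 84 = 8 days.

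**Step 2: size among patients who attend Week 13 (assumed inputs).** Assume exponential relapse with a median of 56 days after last dose. A fraction f stops at Day 43 in control and attends Week 13 on Day 85, 42 days later. Those who have relapsed by then are not in CDA. Completers have no gap, and there is no censoring before 57 days.

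- True 57-day relapse: 1 − 0.5^(57/56) = 50.6%.
- Early stoppers relapsing before Week 13, hence dropped: 1 − 0.5^(42/56) = 40.5%; kept: 59.5%.
- 57-day relapse in those kept: 1 − 0.5^(15/56) = 16.9%.
- Reported rate: [0.595 f × 0.169 + (1 − f) × 0.506] / [0.595 f + (1 − f)].

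| f | Reported 57-day relapse (true 50.6%) |
|---|---|
| 5% | 49.6% |
| 10% | 48.5% |
| 25% | 45.0% |
| 40% | 41.1% |

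**Step 3: patients without a Week 13 visit (assumed inputs).** Suppose 18 patients are in CDA at Week 13 and 7 relapse: 7/18 = 38.9%. Adding back 3 excluded patients with prior CDA gives 7/21 = 33.3% if none relapse and 10/21 = 47.6% if all do. With 5 added back the range is 7/23 = 30.4% to 12/23 = 52.2%. If they relapse at the same rate, the figure stays at 38.9%. The exclusion lowers the rate only if those excluded relapse more often than those kept.

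**Step 4: table against listing.** The two formulas differ by the Week 13 visit day minus the last dose day. For completers with the visit on or after the last dose, that is 0 days (both on Day 85) to 8 days (Days 84 and 92). For early stoppers seen on Day 85, it is 28 days (last dose Day 57), 56 days (Day 29) or 70 days (Day 15).

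**The case against.** A Week 13 responder analysis is a recognisable choice, and Part A SAP 8.2.7 likewise restricts cumulative steroid use to 12-week completers. That would be a sufficient answer if the endpoint were labelled so and the clock started at Week 13. It is neither.

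The number affected may be small. The Part A discontinuation rules in Protocol Appendix 1A concern flare, severe disease or lack of response, so patients stopped under them would mostly not be in control at last dose. Protocol 2.3 reports no discontinuations for treatment-related adverse events among the first 21 patients. This stands, and it is why the 25% and 40% rows cannot be taken as expected values.

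Several stronger readings are tempting, but the documents do not support them:

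- **That all early stoppers are excluded.** The exclusion depends on the Week 13 visit. An early stopper who attends in CDA or CR is kept.
- **That every relapse before Week 13 is wrongly ignored.** In patients who complete 12 weeks these occur on treatment and lie outside an after-stopping endpoint.
- **That the clock mismatch understates relapse.** It changes reported times, not which relapses count.
- **That the table cannot be rebuilt from its listing.** Listing 16.2.4.1.9 carries the last dose date, the relapse or censoring date, and CDA and CR at Week 13. Only its derived time column uses another origin.
- **That the footnote defines a rival population.** The table's row heading and the footnote can apply together; the wording is loose.
- **That there is no other evidence on durability.** Part A also summarises CDA and CR by visit to Week 25, duration of CR and disease scores at follow-up visits, and it lists relapse status by visit.

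**Conclusion.** The rule contradicts its own endpoint, and the guaranteed relapse-free time for a retained early stopper follows from the dates alone. Relapse can be understated for patients who discontinue early. The documents do not show that it is understated overall, because they give neither the number who stop early in control nor any relapse count.

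Under the single assumed model in the working, the loss at 57 days is about 1 to 2 percentage points with 5–10% early stoppers and about 6 points with 25%. For patients who miss Week 13 the direction is not established. Completers lose only relapses falling between last dose and a late Week 13 visit, an interval of up to about 8 days.

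The disagreement between table, listing and figure is a separate traceability error. For a descriptive secondary endpoint in an uncontrolled pilot of up to 25 patients in Part A, this should be corrected, but it does not touch the primary result.

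**What to change.** Use one rule in Part A SAP 8.2.6, Tables 14.2.3.4.x, Figures 14.2.3.4.x and Listing 16.2.4.1.9:

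- **Risk set:** patients in CDA (separately, in CR) at their last PRN1008 dose, whenever that falls.
- **Origin:** date of last dose.
- **Event:** first relapse after last dose, at any visit.

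If the Week 13 subset is kept, enter patients into the risk set at the Week 13 visit (delayed entry) and label it a Week 13 responder analysis. Report the number of patients who stopped early in control and how many of them had a Week 13 visit, so that readers can judge the size.

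The cost is SAP and shell wording plus reprogramming of one endpoint. No new data are needed: Listing 16.2.4.1.9 already carries dose dates, and Listing 16.2.4.1.5 carries dated relapse status by visit. Patients who leave the study soon after stopping will be censored early and add little, but they will no longer be dropped by rule.
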